3.0 STUDY OUTCOMES

In main analyses, binary outcomes measures specified at 12 weeks and 24 weeks below under the Composite Strategy in the ICH E9's estimand framework will be assessed.^[2 3] In the Composite Strategy, a successful outcome will be defined as success achieved at 12 or 24 weeks

and study completed without post-baseline treatment switch during 12 or 24 weeks. In the additional analyses, outcome measures specified at 12 weeks and 24 weeks below will be assessed under the Treatment Policy Strategy. In the Treatment Policy Strategy, any post-baseline treatment switch in the study medication is disregarded.

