3.1 Primary Outcome Measure

The proportion of patients with moderate or high disease activity at baseline who achieve a minimal important difference (MID)[4] in CDAI of ≥ 6 (baseline moderate) or ≥ 12 (baseline high) at 24 weeks after study treatment initiation.

The main Composite Strategy analysis examines the proportion of patients with moderate or high disease activity at baseline who achieve a MID[4] in CDAI of ≥ 6 (baseline moderate) or ≥ 12 (baseline high) at 24 weeks after study treatment initiation AND complete study without post-baseline treatment switch. In the additional Treatment Policy Strategy, continuing the study treatment at 24 weeks is not required.

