3.2 Secondary Outcome Measures

Secondary endpoints include the following:

- a) The proportion of patients with moderate or high disease activity at baseline who achieve CDAI ≤ 10 (low disease activity (LDA)) or CDAI ≤ 2.8 (remission) at 12 and 24 weeks after study treatment initiation.
- b) The change in CDAI scores from baseline to 12 and 24 weeks among patients with moderate or high disease activity at baseline who initiate study treatment.
- c) The proportion of patients with moderate or high disease activity at baseline who achieve an MID in CDAI of ≥ 6 and ≥ 12 , respectively, 12 weeks after study treatment initiation.
- d) The proportion of patients with moderate or high disease activity at baseline who achieve a meaningful reduction (defined as ≥ 10 on the scale of 0–100) of patient global assessment (PtGA) compared to the baseline PtGA 12 and 24 weeks after study treatment initiation.
- e) The proportion of patients with moderate or high disease activity at baseline who achieve a minimal clinically important difference (MCID) in RAPID3 (≥ 3.8 on the scale of 0–30)[5] compared to the baseline RAPID3 at 12 and 24 weeks after study treatment initiation.
- f) The proportion of patients with moderate or high disease activity at baseline who achieve an MCID in patient pain visual analogue scale[6] (≥ 1.1 on the scale of 0–10) compared to the baseline pain at 12 and 24 weeks after study treatment initiation.
- g) The proportion of treatment decisions that were guided by PrismRA test results (in the PrismRA arm only).

Proportions for all the binary endpoints assessed at 12 and/or 24 weeks (a, c–f) will be assessed in the Composite Strategy, which will require no post-baseline treatment switch during 12 and 24 weeks, respectively. The additional Treatment Policy Strategy will disregard post-baseline

treatment switch during 12 and 24 weeks for the binary endpoints assessed at 12 and/or 24 weeks (a, c–f).

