3.3 Exploratory Outcome Measures

- a) The proportion of moderate to high disease activity patients that achieve American College of Rheumatology 50% improvement (ACR50) therapeutic response 12 and 24 weeks after study treatment initiation. (In the PrismRA arm only; analysis in the external control arm may only be descriptive in nature if the constructed ACR50 is not sufficiently available in real world data).
- b) The proportion of patients receiving TNFi therapy and non-TNFi b/tsDMARDs as the study treatment at the index date.
- c) The number of patients that stop or change the study treatment due to an intolerance during the 24-week follow-up period (in the PrismRA arm only; analysis in the external control arm will only be a description of any discontinuation or change in the study treatment).

Exploratory Outcome (a) will be assessed in the Composite Strategy, which will require no post-baseline treatment switch during 12 and 24 weeks. In the additional Treatment Policy Strategy, post-baseline treatment switch during 12 and 24 weeks will be disregarded.

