5.4 Handling Missing Data

Missing data will be handled with two approaches: (1) minimizing the chance of missing data in the study design and conduct stages, and (2) handling missing data with statistical methods in the analysis phase.

The following measures will be taken to reduce missing data in the study design.

PrismRA arm: Missing data will be minimized through rigorous conduct of data collection as described in Section 8.9 of the Protocol. See below for the handling of missing follow-up data.

External control arm: At least one observed CDAI measurement in the 3-month period prior to the index date (b/tsDMARD initiation) and at least three observed CDAI measurements in the 12-month period prior to the index date (including the measurements in the aforementioned 3-month period) will be required to ensure patients are selected from practices where CDAI are recorded as a part of routine care.

The following statistical methods will be considered in handling missing data in the analyses.

The rigorous design of the study aims to reduce the amount of missing data in baseline variables. If needed, single imputation [8] of missing baseline characteristics will be used to ensure that all eligible patients are included in the PS model to estimate the probability of treatment [9] for confounding control. Further details of the treatment PS methods are described below in Section 6.3.

Longitudinal outcomes may be unobserved due to patients that are lost-to-follow up ("drop-out"), missed scheduled visits (PrismRA arm), encounters that fall outside of the specified follow up window (external control arm) or not measured during a completed visit. It is anticipated that at 24-weeks roughly 45% of the PrismRA arm and 50% of the external control arm will be missing outcome data. Within each study arm the number and proportion of missing outcomes at

12 and 24-week visits will be described and baseline characteristics of patients with complete versus incomplete outcome data will be compared.

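### SAP 3.0 and 3.1 make study completion part of primary success, but SAP 5.4, 6.3 and 6.3.1 impute patients lost to follow-up; the definition and the missing-data rule should be reconciled

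*SAP*

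**What the plan says.** SAP 3.0 sets the Composite Strategy as the main analysis of the binary outcomes. Success needs the clinical criterion plus "study completed without post-baseline treatment switch during 12 or 24 weeks". SAP 3.1 repeats this for the primary endpoint: MID at Week 24 "AND complete study without post-baseline treatment switch".

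SAP 3.2 words the same strategy differently for the secondary binary endpoints, "which will require no post-baseline treatment switch during 12 and 24 weeks, respectively", and SAP 3.3 follows it: "Exploratory Outcome (a) will be assessed in the Composite Strategy, which will require no post-baseline treatment switch during 12 and 24 weeks". Neither mentions completing the study.

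On missing data, SAP 5.4 states: "Longitudinal outcomes may be unobserved due to patients that are lost-to-follow up". It also lists missed visits in the PrismRA arm, out-of-window encounters in the control arm, and scores not taken at a completed visit. It expects about 45% (PrismRA) and 50% (control) of Week-24 outcomes to be missing. For the primary analysis these are multiply imputed under missing at random, separately by arm, and the binary endpoints are then derived from the continuous scores. SAP 6.3 puts every eligible initiator into the imputation models. SAP 6.3.1 imputes once, then repeats the modelling and pooling for each endpoint and for both strategies.

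**The concern.** The same patient is classified in two ways. Someone lost before Week 24 is a certain failure under the wording of 3.0 and 3.1, and a possible responder under 5.4, 6.3 and 6.3.1. This concerns the main analysis of the primary endpoint.

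The choice matters because retention is produced differently in the two arms: scheduled trial visits on one side, routine-care encounters on the other. If dropout is failure, any difference in dropout becomes part of the estimated effect of the test. If the choice were left until outcomes had been seen, there would be two chances of a positive result.

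A smaller gap sits beside this. No step in 6.3.1 says how switch status is combined with an imputed score, or what to do when switch status was not observed. The imputation model includes dependent variables, which may cover switch status, but it is not named. Protocol 10.5 names treatment status as a possible input and leaves the details to the SAP.

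**Working it through.** **The plan's own figure.** SAP 5.1 states 88% power for 40% vs 30%, with 600 and 1,500 patients before 45% and 50% attrition. Evaluable: 600 × 0.55 = 330 and 1,500 × 0.50 = 750. Exact two-sided Fisher power at 5% is 88.4%, so the figure reproduces. These rates are for MID alone, not for the composite.

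**Inputs.** Missing Week-24 outcome 45% and 50% (SAP 5.1, 5.4); MID rates 40% and 30% (SAP 5.1); about twice as many matched controls as PrismRA patients (SAP 6.3), so 600 vs 1,200; two-sided 5% (SAP 5.3).

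**Assumptions.** The documents do not give the share *d* of missing patients who are true dropouts, so it is varied. Missingness is unrelated to outcome and there is no switching. Covariates and matching weights are ignored.

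**Rules compared.** Rule A: dropouts fail, other missing values are imputed. Rule B: all missing values are imputed. Rejection rates come from simulation (40,000 runs, 40 imputations within arm, log odds ratio pooled by Rubin's rules).

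Expected success under A is p × (1 − 0.45d) for PrismRA and p × (1 − 0.50d) for control.

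*No true effect, p = 30% in both arms, equal d:*

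| d | PrismRA vs control under A | Difference (points) | OR | Rejection, A | A or B rejects |
|---|---|---|---|---|---|
| 25% | 26.6% vs 26.3% | 0.4 | 1.02 | 5.1% | 6.1% |
| 50% | 23.3% vs 22.5% | 0.75 | 1.04 | 6.0% | 7.6% |
| 75% | 19.9% vs 18.8% | 1.1 | 1.07 | 8.0% | 10.0% |
| 100% | 16.5% vs 15.0% | 1.5 | 1.12 | 13.2% | 15.4% |

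Rule B rejects in 4.8–5.0% throughout.

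*No true effect, unequal d:*
- 25% PrismRA, 50% control: 0.30 × (0.8875 − 0.75) = +4.1 points, rejection 34%.
- 50% PrismRA, 25% control: 0.30 × (0.775 − 0.875) = −3.0 points, rejection 20%.

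Unequal *d* is plausible because SAP 5.4 gives different non-dropout reasons for the two arms. The direction is unknown.

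*Planned effect, 40% vs 30%, equal d:*

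| d | Success under A | Difference (points) | OR | Power, A | A and B disagree |
|---|---|---|---|---|---|
| 25% | 35.5% vs 26.3% | 9.25 | 1.55 | 88% | 3.7% |
| 50% | 31.0% vs 22.5% | 8.5 | 1.55 | 90% | 5.8% |
| 75% | 26.5% vs 18.8% | 7.75 | 1.56 | 93% | 8.1% |
| 100% | 22.0% vs 15.0% | 7.0 | 1.60 | 95% | 10.1% |

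Rule B gives 40% vs 30%, OR 1.56, power 86%. The proportions and their difference move far more than the odds ratio.

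**Unseen switches.** Assume a fraction *s* of patients switch, independently of MID, and unseen switches are counted as none. The bias with p = 30% in both arms is 0.30 × s × (0.45 − 0.50): −0.15 points at s = 10% and −0.30 points at s = 20%, with about 4% rejection. This is negligible, and it takes every patient with missing CDAI to have unseen switch status.

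**The case against.** The strongest reply is that dropout-as-failure is the weaker reading. SAP 3.0 contrasts the two strategies only by how they treat a switch, and 3.2 and 3.3 restate the composite without completion. SAP 3.1 describes its alternative in terms of treatment, not retention: "In the additional Treatment Policy Strategy, continuing the study treatment at 24 weeks is not required". Applying study completion at Week 12 makes little sense in a 24-week follow-up. SAP 5.4, 6.3 and 6.3.1 all send dropouts to imputation. This stands: imputation is probably what was meant. It does not remove the contradiction, because the definition of the primary outcome still says otherwise, in two places.

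A reader might go further and infer any of the following. The documents do not support them as grounds for a more serious finding.

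- *The composite has no rule for switching.* SAP 3.1 already makes an observed switch a non-success. What is missing is the explicit derivation line and the case of unobserved status.
- *Unseen switches distort the result.* The calculation above says not. Medication can also be known when CDAI is missing: controls have linked prescription and claims data (SAP 5.2), and PrismRA patients may have EMR access where a release was signed (Protocol 8.9).
- *Stopping without replacement is a further flaw.* SAP 3.3 does separate the two events, "The number of patients that stop or change the study treatment due to an intolerance during the 24-week follow-up period", while the composite mentions only a switch. That is a wording point to settle.
- *Completion is meaningless for controls.* Protocol 8.11 says withdrawal and completion do not apply to them, but SAP 1.0 ends their follow-up at Week 24, death or loss. This is missing detail.

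The Treatment Policy analysis, the complete-CDAI sensitivity analysis (SAP 6.3.2) and the optional analyses in SAP 8.0 help interpretation. None says which rule is the main one.

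**Conclusion.** The contradiction is real and lies in the current text of the primary definition. It should be fixed before outcomes are analysed; confidence is medium, because most of the SAP points to imputation.

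It would be too strong to say that the primary analysis is materially biased as planned. If imputation is applied, false rejection stays near 5% under the assumptions used. If the literal rule is applied, the inflation is small for equal dropout shares up to 50% (5–6%). The larger figures need all missing patients to be dropouts (13%) or unequal shares (34% or 20%), and the documents give no dropout share. What depends most on the choice at the planned effect is the reported proportions: 40% vs 30%, or anything from 35.5% vs 26.3% down to 22% vs 15%, with the odds ratio between 1.55 and 1.60 throughout.

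**What to change.** 1. In SAP 3.0 and 3.1, delete the study-completion wording, so that the composite is MID and no post-baseline switch, as in 3.2 and 3.3. Dropout is then handled by the planned imputation. In the same edit the sponsor should say whether stopping without replacement counts as a switch, and use one term throughout 3.0–3.3.
2. In SAP 5.4 and 6.3.1, state that:
   - switch status by Week 12 and by Week 24 is in each arm's imputation model;
   - an observed switch is a composite failure even if CDAI is missing;
   - switch status still unobserved after using available prescription, claims or EMR data is imputed with the scores;
   - in each imputed dataset the composite is derived from score and switch status, and Treatment Policy from the score alone.
3. In SAP 6.3.2, add dropout-as-failure as a sensitivity analysis, with dropout defined for each arm.

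If the sponsor prefers dropout-as-failure as the main rule, 5.4 must say that dropouts are not imputed for the composite, and dropout must be defined in each arm.

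Cost: a few SAP sentences and two more imputation variables per arm. Protocol 8.6 already schedules or maps the adherence check and current medications at Weeks 12 and 24. No new patients are needed. The price is a missing-at-random assumption for switch status, which may be doubtful if patients leave because they change treatment; the sensitivity analysis in item 3 shows how far the result depends on how dropouts are classified.

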3.2 Secondary Outcome Measures

Secondary endpoints include the following:

- a) The proportion of patients with moderate or high disease activity at baseline who achieve CDAI ≤ 10 (low disease activity (LDA)) or CDAI ≤ 2.8 (remission) at 12 and 24 weeks after study treatment initiation.
- b) The change in CDAI scores from baseline to 12 and 24 weeks among patients with moderate or high disease activity at baseline who initiate study treatment.
- c) The proportion of patients with moderate or high disease activity at baseline who achieve an MID in CDAI of ≥ 6 and ≥ 12 , respectively, 12 weeks after study treatment initiation.
- d) The proportion of patients with moderate or high disease activity at baseline who achieve a meaningful reduction (defined as ≥ 10 on the scale of 0–100) of patient global assessment (PtGA) compared to the baseline PtGA 12 and 24 weeks after study treatment initiation.
- e) The proportion of patients with moderate or high disease activity at baseline who achieve a minimal clinically important difference (MCID) in RAPID3 (≥ 3.8 on the scale of 0–30)[5] compared to the baseline RAPID3 at 12 and 24 weeks after study treatment initiation.
- f) The proportion of patients with moderate or high disease activity at baseline who achieve an MCID in patient pain visual analogue scale[6] (≥ 1.1 on the scale of 0–10) compared to the baseline pain at 12 and 24 weeks after study treatment initiation.
- g) The proportion of treatment decisions that were guided by PrismRA test results (in the PrismRA arm only).

Proportions for all the binary endpoints assessed at 12 and/or 24 weeks (a, c–f) will be assessed in the Composite Strategy, which will require no post-baseline treatment switch during 12 and 24 weeks, respectively. The additional Treatment Policy Strategy will disregard post-baseline

treatment switch during 12 and 24 weeks for the binary endpoints assessed at 12 and/or 24 weeks (a, c–f).

3.3 Exploratory Outcome Measures

- a) The proportion of moderate to high disease activity patients that achieve American College of Rheumatology 50% improvement (ACR50) therapeutic response 12 and 24 weeks after study treatment initiation. (In the PrismRA arm only; analysis in the external control arm may only be descriptive in nature if the constructed ACR50 is not sufficiently available in real world data).
- b) The proportion of patients receiving TNFi therapy and non-TNFi b/tsDMARDs as the study treatment at the index date.
- c) The number of patients that stop or change the study treatment due to an intolerance during the 24-week follow-up period (in the PrismRA arm only; analysis in the external control arm will only be a description of any discontinuation or change in the study treatment).

Exploratory Outcome (a) will be assessed in the Composite Strategy, which will require no post-baseline treatment switch during 12 and 24 weeks. In the additional Treatment Policy Strategy, post-baseline treatment switch during 12 and 24 weeks will be disregarded.

4.0 DEFINITIONS

Terms	Definition of Terms
DRIVE Study	The comparative effectiveness study of the PrismRA test comparing the clinical outcomes of patients in the PrismRA arm (trial) and the external control arm (observational).
Baseline	Assessments of patients as they enter the PrismRA arm. For the external control arm, the corresponding baseline CDAI assessment window is the 3-month period before the index date (defined as the time of study treatment initiation). For medical history all available data before the index date will be used in the external control arm.
Enrollment	The point at which the patient signs the informed consent form for the PrismRA arm. Not applicable for the external control arm.
PrismRA arm	Trial participants in the trial conducted by Scipher Medicine for whom PrismRA test is performed and the Investigator will use the PrismRA test results to inform the treatment decision.
External control arm	OM1 real-world data patients who received standard of care treatment for RA with TNFi or non-TNFi b/tsDMARDs without guidance from PrismRA test results.

Terms	Definition of Terms
Study Treatment	The b/tsDMARDs (FDA approved for RA) that is initiated at Visit 2 (See Protocol Section 8.5) informed by the PrismRA test in the PrismRA arm and as a part of standard of care in the external control arm. This study treatment (b/tsDMARDs) can be the very first b/tsDMARD for the patient or a subsequent b/tsDMARD after having used one or more TNFi bDMARDs (but not non-TNF β b/tsDMARDs).
Study Treatment Initiation	The point at which a study treatment (See “Study Treatment” above) is initiated to treat RA. This time point constitutes the index date (beginning of the follow-up) and defined as Visit 2
RA Disease Activity	
Disease activity is based on the CDAI score as follows:
 
 • Remission: CDAI \leq 2.8 • Low: CDAI > 2.8 and \leq 10.0 • Moderate: CDAI > 10.0 and \leq 22.0 • High: CDAI > 22.0 
For the PrismRA arm, the CDAI scores will be assessed by the Investigator. The CDAI scores for the external control arm in OM1 PremiOM RA consist of CDAI scores in structured EMR data, and CDAI scores estimated by machine learning based on unstructured data.^[7] CDAI scores from all data sources will be used.

TNFi-naïve subgroup	Patients who have never taken a TNFi prior to visit 2.
TNFi-exposed subgroup	Patients who had received at least one TNFi prior to visit 2.

5.0 GENERAL STATISTICAL CONSIDERATIONS

5.1 Sample Size and Power Calculations

The study is powered to detect a difference of 10% in the proportion of patients with improvement in CDAI from baseline to Week 24 by at least the MID as defined in Section 3.1 between the PrismRA arm and the external control arm. Results are shown in **Table 1**. It is estimated that the attrition rate at Week 24 (defined as the proportion of patients with missing CDAI scores at Week 24 for any reason) can be up to 45% in the PrismRA arm and up to 50% in the external control arm. The sample sizes below have been inflated accordingly to account for the patient attrition mentioned above.

With a sample size of 600 in the PrismRA arm and 1,500 in the external control arm, the study has 88% power to establish the superiority of the PrismRA intervention as compared to the standard of care by detecting a difference of 10% between the two study arms based on Fisher’s

exact test of independent proportions assuming the proportion of patients with improvement in CDAI by MID are 40% and 30% in the PrismRA arm and the external control arm, respectively.

Table 1. Study power for comparing proportion of patients with improvement in CDAI from baseline by at least MID between the two study arms

Sample size in the PrismRA arm before attrition	Sample size in the external control arm before attrition	Proportion of patients in the PrismRA arm with MID improvement in CDAI	Proportion of patients in the external control arm with MID improvement in CDAI	PrismRA arm, attrition			
				30%	35%	40%	45%
				Study power			
600	1,000	0.45	0.35	86%	84%	82%	80%
600	1,000	0.40	0.30	87%	86%	84%	82%
600	1,000	0.35	0.25	90%	89%	87%	85%
600	1,500	0.45	0.35	91%	90%	88%	86%
600	1,500	0.40	0.30	92%	91%	89%	88%
600	1,500	0.35	0.25	94%	93%	92%	90%
600	2,000	0.45	0.35	93%	92%	90%	88%
600	2,000	0.40	0.30	95%	93%	92%	90%
600	2,000	0.35	0.25	96%	95%	94%	92%

The sample size calculation was performed with SAS (version 9.4, Cary, NC).

5.2 Analysis Populations

PrismRA arm:

This arm will enroll approximately 600 RA patients at approximately 33 clinical sites who are at least 18 years of age. All patients in the PrismRA arm will undergo PrismRA testing at their first study visit (Visit 1). See Section 6.1.1 and 6.1.2 for patient inclusion and exclusion criteria for details.

This study will perform analyses for two sets of populations from the PrismRA arm. The first one is the modified ITT analysis population, which consists of patients that initiate the study

treatment at Visit 2. A sub-population of patients who are adherent to the PrismRA test results will also be analyzed. This sub-population will exclude patients who initiated TNFis despite having a PrismRA result indicating a molecular signature of non-response to TNFi therapies.

External control arm:

Patients with RA in the OM1 PremiOM RA Dataset will be selected based on the same eligibility criteria as in the PrismRA arm and adapted for real-world data availability where necessary. Patients in the external control arm will be balanced with patients in the PrismRA arm using a propensity score (PS) model developed with the primary goal of achieving balance in baseline characteristics between the comparison groups. The external control arm is expected to have at least 1,500 eligible patients, with no less than 750 patients having CDAI scores at both baseline and Week 24. Data from patients who initiated b/tsDMARDs in the contemporaneous period (March 2022 and onward) will be used and if needed, the recent historical period (6-month to 3-year period prior to March 2022) will be used to maximize the size of the patient pool while minimizing confounding by the potential secular trends in treatment patterns. The PS model building process will aim to retain the inclusion of as many PrismRA arm participants as possible. If less than 95% of the PrismRA arm is included due to the lack of a matched control or non-overlapping PS, the historical period will be used for identifying external control patients. The smallest historical time window that can retain inclusion of greater than 95% of PS matched PrismRA patients will be used. The overlap in PS distributions between the external control and PrismRA arms will inform the ultimate sample size.

The data source for the analysis is the OM1 PremiOM RA Dataset within the OM1 Real-World Data Cloud (RWDC [OM1, Inc, Boston, MA, US]). The OM1 RWDC is derived from deterministically linked, de-identified, individual-level health care claims, electronic medical record (EMR), and other data. EMR data are from sources geographically representative of the U.S. population and include medication history and prescription information, laboratory results, and diagnoses as documented by a physician. Additional medical and pharmacy claims data are linked to the clinical data to fill gaps in patients' clinical care. The medical and pharmacy claims contain billing and coding history on inpatient and outpatient encounters from acute care facilities, ambulatory surgery centers, and clinics. The OM1 RWDC includes data from January 2013 to present day.

To qualify for the OM1's PremiOM RA dataset, each patient must be at least 16 years old at the time of the qualifying diagnosis and meet at least one of the following conditions:

- At least two diagnosis codes for RA, at least 30 days apart, each coming from an encounter with a rheumatologist
- At least one inpatient RA diagnosis code
- At least two outpatient RA diagnosis codes, at least 30 days apart and within a year, regardless of physician specialty
- At least one outpatient RA diagnosis code and a prescription or fill for a DMARD and no diagnosis for any of the non-RA conditions for which those drugs may also be prescribed

Non-RA conditions are defined as juvenile idiopathic arthritis, psoriatic arthritis/psoriasis, ankylosing spondylitis, Crohn's disease, ulcerative colitis, hidradenitis suppurativa, cryopyrin-associated periodic syndromes, renal transplant, malaria, systemic lupus erythematosus, giant cell arteritis, cytokine release syndrome, all cancers, hydatidiform mole.

